13.0 STATISTICAL METHODS

13.1 Statistical and Analytical Plans

A statistical analysis plan (SAP) will be prepared and finalized prior to unblinding of subject's treatment assignment. Unblinding of subject's treatment assignment will only occur after database lock. This document will provide further details regarding the definition of analysis variables and analysis methodology to address all study objectives.

A blinded data review will be conducted prior to unblinding of subject's treatment assignment. This review will assess the accuracy and completeness of the study database, subject evaluability, and appropriateness of the planned statistical methods.

13.1.1 Analysis Sets

The Full Analysis Set (FAS) will consist of subjects who received at least one dose of investigation product. Subjects in the FAS population will be analysed according to their original treatment assignment regardless of the treatment received.

The safety analysis set will consist of subjects who received at least one dose of investigational product. Subjects in the safety population will be analysed according to their treatment received, regardless of treatment assigned; subjects who received ≥ 1 dose of CER 15 mg will be analyzed in the CER 15 mg treatment group.

The per-protocol (PP) analysis set will consist of subjects no major protocol violations, and who received at least 1 dose of investigational product.

13.1.2 Analysis of Demographics and Other Baseline Characteristics

All data collected in this study will, where applicable, be summarised by treatment regimen using descriptive statistics. For continuous variables mean values, standard deviations, median and lower and upper percentiles, minimum and maximum will be calculated. For categorical variables frequencies and percent will be calculated.

13.1.3 Efficacy Analysis

All efficacy analyses will be based on an FAS subject population. The primary efficacy endpoint will also be analysed using the PP subject population. Unless otherwise specified, all statistical tests will be conducted against a 2-sided alternative hypothesis at the 0.05 level of significance.

For all efficacy evaluations, if the subject discontinued the double-blind treatment phase prior to Day 15, the last available post treatment (final) evaluation was used to estimate the remaining missing evaluations (ie, last observation carried forward [LOCF]). For reference, the observed values were summarized and analyzed using the same methods as the LOCF values.

Primary Efficacy Endpoints

For the primary efficacy analysis, the subject's rating of medication helpfulness at Day 3 will be analyzed for the difference between the Placebo and the 15mg CER treatment group using a 2-sample Wilcoxon rank sum test. The primary end point is a 5-point ordinal rating scale from 0=Poor to 4=Excellent. This study will evaluate differences between Placebo and CER treatment on the percentages for each of the 5-grade scale categories. Therefore, the 2-sample Wilcoxon sum rank test

will compare the shift of ordinal distributions of responses in both treatment groups. Only differences between the treatment groups at the significance level of 0.05 will be considered statistically significant. Frequency counts and percentages showing the distribution of the subject's rating of medication helpfulness at Day 3 will be provided to summarize these parameters.

A supportive analysis on responders will be done to confirm the results of the primary analysis. A responder will be defined as a subject who had a rating of either "very good" or "excellent" for the subject's rating of medication helpfulness at Day 3. A continuity-adjusted Chi-square test will be used to compare the number of "responders" between the Placebo and the CER treatment group. The number and percent of subjects who met the definition of responder at Day 3 will be presented.

The primary analysis and supportive analysis will be repeated for day 7 and day 14.

Trends in the distribution of ratings by treatment group will be compared across the 3 visits to determine if there were any qualitative differences in the pattern of treatment response. Differences between treatments in the distribution of ratings at the 3 visits will be analysed using a weighted least squares model for marginal homogeneity including a parameter for treatment and treatment-by-visit interaction. Trends over time in the proportion of responders among the treatment groups will be assessed qualitatively by comparing the patterns of change in proportion of responders from Day 3 through Day 14. Repeated-measures analysis of proportions using Generalized Estimating Equations (GEE) will be used for comparisons among treatments of the trend in proportion of responders over time.

Time to improvement in subject's rating of medication helpfulness will be defined as the number of days from the start of treatment to the first time there was an assessment of "fair" to "excellent". If the subject did not have any improvement in their rating of medication helpfulness, time to improvement was censored and equaled the number of days from the start of treatment to the last measurement during the study. The Kaplan-Meier curves will be compared using the generalized Wilcoxon test for survival analysis.

Secondary Efficacy Endpoints

The following subject's ratings will be analyzed and summarized: relief from local pain due to muscle spasm, restriction in activities of daily living, restriction of movement, and clinical global impression. Time to improvement of subject-rated relief from local pain will be analyzed.

Subject Ratings

The subject's ratings will be analyzed separately for the differences between the Placebo and CER treatment group using a 2-sample Wilcoxon rank sum test.

Time to improvement of subject-rated relief from local pain will be defined as the number of days from the start of treatment to the first time there was an assessment of "a little relief" to "complete relief". If the subject did not have any improvement in their rating of relief from local pain, time to improvement was censored and equaled the number of days from the start of treatment to the last measurement recorded for the subject during the study. The Kaplan-Meier curves will be compared using the generalized Wilcoxon test for survival analysis.

Other Efficacy Endpoints

The physician's clinical global assessment on Days 3, 7 and 15 of treatment will be analysed in the same way as the primary endpoint.

The following physician-rated assessments will be summarized: presence of muscle spasm, presence of local pain, limitation of range of motion, and limitation of activities of daily living. Frequency counts and percentages showing the distribution of the above physician's assessments at Days 1, 3, 7, and 15 are provided to summarize these parameters.

Company Confidential Information

For efficacy evaluations, End of Study was defined as Day 15, or if the subject discontinued the double-blind treatment phase prior to Day 15, the last available post treatment evaluation was used to estimate the remaining missing evaluations (ie, LOCF).

If the assumptions underlying planned inferential methods are not adequately met, methods will be amended as needed for appropriate analysis.

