Note: If the subject is found to be pregnant, the subject must be withdrawn immediately. The procedure is described in Section 9.1.11.

7. Lack of efficacy. The necessity to use rescue medication (any analgesics) AND/OR the investigator has determined that the subject is not benefiting from investigational treatment and, continued participation would pose an unacceptable risk to the subject.

8. Other.

Note: The specific reasons should be recorded in the "specify" field of the (e)CRF.

CONFIDENTIAL

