8.1.1.2 Rescue Medication

NSAIDs, topical over-the-counter medications and other analgesics will be allowed as rescue therapy only and to be used before the subject is discontinued due to lack of efficacy.

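### Both time-to-improvement analyses censor unimproved subjects at their last measurement even when they stop for lack of efficacy or rescue, so the censoring is informative and each arm's Kaplan-Meier improvement rate is overstated

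*Protocol*

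**What the plan says.** Protocol Section 13.1.3 defines two time-to-improvement variables. Each is the "number of days from the start of treatment to the first time there was an assessment of" a threshold rating: *fair* or better for medication helpfulness, and *a little relief* or better for relief from local pain. These are the lowest steps above the bottom of each scale.

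For a subject who never reaches the threshold on helpfulness, "time to improvement was censored and equaled the number of days from the start of treatment to the last measurement during the study". For relief from local pain, censoring likewise runs "to the last measurement recorded for the subject during the study". For both variables, "The Kaplan-Meier curves will be compared using the generalized Wilcoxon test for survival analysis".

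Three other provisions bear on this:

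- Section 7.5 lists as a discontinuation reason: "Lack of efficacy. The necessity to use rescue medication (any analgesics) AND/OR the investigator has determined that the subject is not benefiting" from treatment.
- Section 8.1.1.2 places rescue ahead of that discontinuation: "NSAIDs, topical over-the-counter medications and other analgesics will be allowed as rescue therapy only".
- The general missing-data rule in Section 13.1.3 is LOCF. After early discontinuation, "the last available post treatment (final) evaluation was used to estimate the remaining missing evaluations".

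**The concern.** Kaplan-Meier and the generalized Wilcoxon test assume that a censored subject has the same later chance of the event as subjects still at risk. A subject who has rated every day *poor*, or *no relief*, and stops on Day 5 for lack of efficacy or rescue is censored on Day 5 precisely because of not improving. From then on the estimator treats that subject like those who stayed, which is implausible given the recorded reason for leaving.

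Two things are at stake. Each arm's curve overstates improvement relative to counting these leavers as not improved. In addition, if one arm loses more subjects this way, its curve is inflated more, so the gap between the arms narrows and the test loses part of the difference.

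The LOCF sentence also treats the same subject differently. Carried forward, the bottom rating would last to the end of treatment, whereas the censoring rule stops follow-up on Day 5. The protocol does not say which governs the time-to-event derivation.

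**Working it through.** **Plan figures.** The protocol states no figure for the time-to-improvement analyses and no share of dropout due to lack of efficacy. The nearest figure is in Section 13.3: 77 evaluable per group and 15% all-cause dropout, giving 77/0.85 = 90.6 against the stated 90. So 15% of an arm is 0.15 × 90 = 13.5 subjects, 5% is 4.5 and 2.5% is 2.25.

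**Inputs for the size of the effect.** From Section 9.3.2: daily diary for 14 days, with helpfulness and relief rated from Day 2, so 13 rating days. Assumed: 25% of subjects never improve; the rest improve with daily hazard h of 0.2, 0.35 or 0.5; a share d of all subjects (drawn from the 25%) leaves for lack of efficacy, spread evenly over Days 3 to 7.

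**Formulas.**

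- As written: improvement by Day 14 = 1 − ∏(1 − e_t/r_t) over t = 2,…,14. Here e_t = h·O_t, O_t is the number of eventual improvers not yet improved, and r_t is O_t plus the never-improvers still in follow-up.
- Leavers kept at risk as not improved: 0.75 × [1 − (1 − h)^13].

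**Worked case, h = 0.2, d = 5%, 90 subjects.** There are 67.5 eventual improvers and 22.5 never-improvers, of whom 4.5 leave. On Day 8, 17.69 eventual improvers remain and 0.2 × 17.69 = 3.54 improve. As written the risk set is 17.69 + 18.0 = 35.69, a daily rate of 9.9%. With leavers kept it is 17.69 + 22.5 = 40.19, a rate of 8.8%. Multiplied through to Day 14, the result is 73.5% as written against 0.75 × (1 − 0.8^13) = 70.9%, a gap of 2.6 points.

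**Overstatement at Day 14, in percentage points:**

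| Leaving unimproved for lack of efficacy | h = 0.2 (kept: 70.9%) | h = 0.35 (kept: 74.7%) | h = 0.5 (kept: 75.0%) |
|---|---|---|---|
| 2.5% | 1.2 | 0.9 | 0.5 |
| 5% | 2.6 | 2.0 | 1.1 |
| 7.5% | 4.1 | 3.1 | 1.7 |
| 15% | 9.5 | 7.8 | 4.4 |

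**Dependence on the model.** A second model drops the 25% assumption: everyone who stays has a daily chance of 0.05 to 0.30, and the leavers, who never improve, go after Day 3 or Day 7. The overstatement is then 0.6 to 2.0 points at 2% leaving, 1.5 to 4.9 at 5% and 4.5 to 14.7 at 15%. It is positive in every case.

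**Effect on the test.** Second model, 90 per arm, leaving after Day 3, 1,500 simulated trials per row. Positive Z favours CER.

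| Daily chance among stayers, placebo / CER | Leaving, placebo / CER | Mean Z as written | Mean Z, leavers kept at risk |
|---|---|---|---|
| 0.20 / 0.20 | 10% / 10% | 0.04 | 0.03 |
| 0.20 / 0.20 | 15% / 5% | 0.43 | 1.08 |
| 0.20 / 0.20 | 5% / 15% | −0.47 | −1.12 |
| 0.20 / 0.28 | 15% / 5% | 2.46 | 2.90 |
| 0.20 / 0.28 | 5% / 5% | 2.14 | 2.04 |

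With unequal losses, the rule as written pulls Z towards zero whichever arm loses more. In the fourth row the share of significant results is 70% as written against 84%. With equal losses the change is small.

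**The case against.** Censoring at the last observation is the conventional default, and several objections have force.

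- **Few subjects may be affected.** The threshold is one step up the scale, rated daily. Only a leaver who never once reached it matters, and nothing in the protocol supports 25%, or any other share, as never improving. This stands, and it is why the size can only be given as a range.
- **Large illustrations use up the dropout allowance.** The 15% row leaves nobody to stop for adverse events, loss to follow-up or other withdrawal. A reader might take a gap of 9 points or more as the expected bias. The protocol does not support that; it is the extreme of the range.
- **The LOCF rule is not contradicted.** A reader might infer that the two rules conflict outright. LOCF fills in missing ratings, whereas the censoring rule is a specific rule for a derived time, and a specific rule can stand beside a general one. What remains is that they treat the same subject differently and the protocol does not say which governs.
- **The comparison may not be biased.** With equal losses it is nearly unaffected. A reader might infer that the rule favours, or penalises, CER, but nothing in the protocol says which arm will lose more.
- **The alternative has its own assumption.** Keeping leavers at risk supposes that they would not have improved by Day 14. It also relies on the recorded reason, and Section 7.5 itself recognises that voluntary withdrawal may have lack of efficacy behind it. This stands as a cost of the fix.

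Section 13.1.3 also allows methods to be amended if assumptions are not met, but it names no alternative, so it does not cure a rule that the protocol has already fixed.

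**Conclusion.** The point holds as a modest one. The protocol fixes outcome-dependent censoring in both time-to-improvement analyses. Each arm's improvement rate is overstated relative to counting lack-of-efficacy leavers as not improved. With 25% never improving and hazards of 0.2 to 0.5, that is about 0.5 to 2.6 points at 2.5 to 5% leaving, and up to about 9.5 points only if the entire 15% dropout is of this kind. All of these inputs are assumptions except the diary schedule and the 15%. The second model gives larger figures at the same shares, but the same direction.

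The between-arm test is distorted only if losses differ, and then towards hiding the difference. These analyses are not primary, and neither variable appears among the endpoints visible in Section 5.2. The Day 3 primary test, the responder analysis and the sample size are untouched.

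**What to change.** In Section 13.1.3, for both time-to-improvement variables:

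1. Keep subjects who discontinue for lack of efficacy or rescue without prior improvement in the risk set as not improved, censored at Day 14.
2. Censor at the last measurement only for other reasons for leaving.
3. Retain the present rule, censoring everyone at the last measurement, as a sensitivity analysis.
4. State that this rule, and not the LOCF sentence, governs the time-to-event derivation.

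The cost is a sentence or two of text and one derivation rule, with no new data and no change to how subjects are managed. The downside is the assumption that these subjects would not have improved by Day 14, together with reliance on the recorded reason for leaving. The sensitivity analysis shows how much the result depends on that choice.

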5.2.2 Secondary Endpoints

- The percentage of subjects with physician's clinical global assessment on Day 3 of treatment.
- The percentage of subjects with subject's rating of medication helpfulness impression on Day 7 and 14 of treatment.
- The percentage of subjects with physician's clinical global assessment on Day 7 and 15 of treatment.
- The percentage of subjects with subject-rated global impression (relief from local pain, restriction in activities of daily living, restriction of movement, intensity of local pain) of on Day 3, 7 and 14 of treatment.
- The percentage of subjects defined as responders on Day 3, 7 and 14 of treatment.
- The percentage of subjects with physician rated assessment of presence of muscle spasm, presence of local pain, limitation of range of motion, limitation of activities of daily living on Day 3, 7 and 15.

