Assessment of the subject’s answers will be made for the Day 3, 7 and 15.

- **The subject-rated intensity of local pain:**

Subjects will be asked to assess on a daily basis (in the daily diary) their intensity of local pain due to the muscle spasm (in either the lower back or cervical spine) using the following digital rating scale. It is necessary to mark the intensity of pain by circling a one of the 11 points from 0 "No Pain" to 10 "Severe Pain" with an intermediate value of 5 - "Moderate Pain".

Facial pain scale is presented to help the patient to identify the primary area of the intensity of the pain experienced:

Assessment of the subject’s answers will be made for the Day 3, 7 and 15.

- **Subject-Rated Clinical Global Impression:**

[figure not shown]
Subjects will be asked to assess on a daily basis (in the daily diary) their clinical global impression of change compared to Baseline, based on rating on medication helpfulness, relief from local pain, restriction in activities of daily living, restriction of movement.

Assessment of the subject’s answers will be made for the Day 3, 7 and 15.

Company Confidential Information

Company Confidential Information

Company Confidential Information

- Hematology, blood chemistry, urinalysis, urine pregnancy testing (if applicable), vital signs, physical examinations, and ECGs will be performed at Screening and study termination. Vital signs will be recorded at each clinic visit. Monitoring and recording of AEs will be performed during each clinic visit and continued for 3 weeks after the last dose of study drug.

Other assessments:

- **Presence of muscle spasm**

The physician was asked to evaluate the presence of muscle spasm by palpation (increased consistency of a muscle or group of muscles) using the following 5-point rating scale at each visit:

“1 = none” (no muscle spasm present)

“2 = mild” (the muscle is somewhat harder than usual)

“3 = moderate” (muscles are hard and borders of increased consistency can be determined by palpation)

“4 = moderately severe” (muscles are very hard and borders are sharply defined by palpation)

“5 = severe” (board-like hardness of the muscles)

- **Presence of local pain**

The physician was asked to assess the presence of local pain due to muscle spasm by palpation (tenderness on palpation) using the following 5-point rating scale at each visit:

“1 = none” (no pain)

“2 = mild” (complaint of local discomfort on palpation)

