9.3.2 Randomization

Randomization will take place on Day1 (could be the same day at which Screening visit took place). The following procedures will be performed and documented during Randomization:

- Vital Signs (if not same day as Screening procedures).
- Concomitant medications.
- Adverse Events.
- The following parameters will be assessed by the investigator: presence of muscle spasm, presence of local pain, limitation of activities of daily living, and limitation of range of motion.
- Subject Diary dispense. Subjects should be instructed :
 - To complete assessment for Day 1 at the hospital before the first drug intake.
 - Starting from Day 2 record the following assessments (compared to Baseline) in the daily diary: rating of medication helpfulness, relief from local pain, subject-rated Clinical global impression, restriction in activities of daily living, and restriction of movement;
 - To record the following assessments in the daily diary: **Company Confidential Information** intensity of local pain **Company Confidential Information** ;
 - To complete their diary during 14 days at the same time each day if possible but record the worst feeling/symptom since the diary was last completed. No diary to be completed at Day 15 (Visit 4) but returned to the Investigator.
 - To bring their diary to each study visit for review by Investigator. Completed pages will be collected by Investigator, then the diary will be dispensed to subject again.
- If the subject has satisfied all of the inclusion criteria and none of the exclusion criteria for randomization, the subject should be randomized using the IVRS/IWRS, as described in Section 8.2.
- Study drug dispense. The medication identification (ID) number of the study drug will be provided via IVRS/IWRS. To avoid any overdose and non-compliance with study drug intake, original bottle containing 60 capsules with CER 15 mg or Placebo will be opened in front of the subject and 40 capsules of 60 will be removed in cleanliness condition and put into the additional bottle for keeping at the site (never dispensed to subject) until destruction. Original bottle containing 20 capsules with CER 15 mg or Placebo will be dispensed to subject. Subject will be instructed to:
 - To swallow one capsule whole with 180 mL of room temperature water, once daily in the evening between 18:00 and 19:00 starting from Day1.

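### Pain intensity (0 to 10) is a secondary endpoint that the readable analysis list in 13.1.3 does not name, and the one readable test that could reach it makes no use of the Day 1 score

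*Protocol*

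**What the plan says.** **Endpoint.** Section 5.2.2, like the study summary in Section 2.0, includes pain intensity among the subject-rated secondary endpoints: "restriction of movement, intensity of local pain) of on Day 3, 7 and 14 of treatment".

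**Scale.** Section 9.1.6 makes it an absolute numeric level: "It is necessary to mark the intensity of pain by circling a one of the 11 points from 0". The bottom of the range stands for absence of pain and the top, 10, for severe pain.

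**Timing.** Section 9.3.2 tells subjects "To complete assessment for Day 1 at the hospital before the first drug intake". Separate instructions follow for two groups of diary items. The first group is "Starting from Day 2 record the following assessments (compared to Baseline) in the daily diary: rating of medication helpfulness, relief from local pain", together with global impression, daily activities and movement. Pain intensity is in the second group, between redactions, and carries neither the Day 2 start nor the comparison with baseline.

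**Analysis.** Under Secondary Efficacy Endpoints, Section 13.1.3 states "The following subject's ratings will be analyzed and summarized: relief from local pain due to muscle spasm, restriction in activities of daily living" and ends the list with "restriction of movement, and clinical global impression. Time to improvement of subject-rated relief from local pain will be analyzed". Under Subject Ratings it then assigns the subject's ratings a two-sample Wilcoxon rank sum test, with no baseline term, stratum or change score mentioned.

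**The concern.** The endpoint section and the analysis section do not line up. Whoever writes the detailed analysis cannot tell from the readable text whether pain intensity was left out on purpose, overlooked, or placed elsewhere.

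If the general reference to the subject's ratings is taken to include it, the method fits less well than it does for its neighbours. Relief, daily activities, movement and global impression are rated against baseline by construction, so an unadjusted rank test suits them. Pain intensity is a level, and the entry criteria in Section 7.1 set no minimum pain score, so subjects may start from quite different levels. A test on follow-up scores alone leaves that starting variation in the error term.

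At stake is the precision of one secondary comparison, on the only visible patient-reported measure of pain level in a trial of acute pain.

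**Working it through.** **1. The two lists side by side.**

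| Subject rating | Secondary endpoint, 5.2.2 | Readable list, 13.1.3 |
|---|---|---|
| Relief from local pain | yes | yes |
| Restriction in daily activities | yes | yes |
| Restriction of movement | yes | yes |
| Intensity of local pain | yes | not named |
| Clinical global impression | yes, as the umbrella term | yes |

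Section 5.2.2 places intensity in a bracket after the global impression, so one could ask whether analysing the global impression covers it. Section 9.1.6 answers no: it bases that impression on helpfulness, relief, daily activities and movement, and defines intensity as a separate item. The endpoint is also worded as a percentage of subjects, which does not suit a 0 to 10 score.

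**2. What other text could cover it.** Section 13.1.2 promises descriptive summaries of all data, which is not a between-group comparison. Section 13.1.3, Other Efficacy Endpoints, contains a redacted paragraph whose content is unknown.

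**3. Is there a baseline score?** Section 9.3.2 has a diary assessment before the first dose and puts no later start on intensity. A Day 1 value is therefore implied, though not itemised, and no row for intensity can be read in Appendix A.

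**4. The plan's own figures.** None concerns pain intensity: no effect, standard deviation or power is given for it. The 77 evaluable subjects per arm in Section 13.3 belong to medication helpfulness, and the study 1106 distribution behind them is not shown, so 77 cannot be recomputed. The dropout step can: 77 / (1 − 0.15) = 90.6, against 90 stated. No stated figure is shown to be wrong.

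**5. Illustration of the precision given up.** Assumptions, none of them from the protocol:
- the unadjusted comparison has 80% power at two-sided 0.05;
- the correlation r between the Day 1 and follow-up scores is 0.4, 0.5 or 0.6;
- variance is equal at both times;
- the rank-test efficiency factor is the same with and without adjustment, so it cancels.

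The standardised signal at 80% power is 1.960 + 0.8416 = 2.8016. With relative variance V, power = Φ(2.8016/√V − 1.960). Here V = 1 for the follow-up score alone, 1 − r² after adjustment, and 2(1 − r) for a plain change score.

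| r | Adjusted V = 1 − r² | Equivalent gain in n, 1/V − 1 | Power, adjusted | Power, change score |
|---|---|---|---|---|
| 0.4 | 0.84 | 19% | Φ(1.097) = 86% | 73% |
| 0.5 | 0.75 | 33% | Φ(1.275) = 90% | 80% |
| 0.6 | 0.64 | 56% | Φ(1.542) = 94% | 88% |

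Over a wider range of r, 0.3 to 0.7, adjusted power runs from 84% to 98%. The change score falls below the unadjusted 80% whenever r is under 0.5, so it is not a safe substitute for adjustment.

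**The case against.** The strongest reply is that the analysis may be there but blacked out. Position does not exclude this: the physician's global assessment and the four physician ratings are secondary endpoints in Section 5.2.2, yet they are analysed under Other Efficacy Endpoints, next to the redacted paragraph. Nor is pain intensity readable everywhere else. The efficacy variables in Section 6.1 run into a redaction after restriction of movement, and the surviving Appendix A rows show the four listed ratings with redacted rows before and after. This stands. A reader might infer that the protocol gives its pain score no between-group analysis, but the documents do not support that.

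The general wording under Subject Ratings can also take in a measure that Section 9.1.6 calls subject-rated. That too stands, and it leads to the unadjusted test.

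On the baseline, the text does not say whether raw scores or changes would be ranked. Section 13.1 defers variable definitions and methods to a statistical analysis plan, and an unadjusted rank test is valid under 1:1 randomisation. All of this is right. A reader might infer a biased comparison; there is none. What remains is that the readable method is less precise than one the trial could apply to data it already appears to collect.

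Finally, pain is not otherwise neglected: subject-rated relief gets both a Wilcoxon test and a time-to-improvement comparison. That lowers the priority without removing the mismatch.

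**Conclusion.** The point holds in a limited form. A named secondary endpoint does not appear in the readable secondary analysis list, and the passages need reconciling. Whether it is truly missing cannot be settled, because redacted text may cover it.

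The only readable between-group test that could apply does not use the implied Day 1 score. The cost is precision, not validity: about 6, 10 or 14 points of power at correlations of 0.4, 0.5 or 0.6. Both those correlations and the 80% starting power are assumptions, so the figures show the usual worth of baseline adjustment and do not measure a loss in this trial. They also rest on the Day 1 pain score being recorded, which Section 9.3.2 implies. This is a low-priority improvement.

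**What to change.** In Section 13.1.3, name intensity of local pain in the secondary list, or state where it is already analysed. Specify the comparison at Days 3, 7 and 14 as ANCOVA, or rank ANCOVA if the score distribution calls for it, with the Day 1 pre-dose score as covariate. Where ANCOVA is used, report the adjusted difference between arms with its 95% confidence interval. Do not replace adjustment with a plain change from baseline. Confirm in Section 9.3.2 and Appendix A that the Day 1 assessment includes pain intensity.

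The cost is wording only, settled before unblinding. No new data are needed provided the Day 1 score is collected as implied.
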